Description of change	R16 0342 _____ Bohnsack O, Hees A, Ludajic K. Adaptation of the immune related response criteria: inRECIST. ESMO 2014. Ann Oncol. 2014; 25(suppl_4): iv361 iv372. 10.1093/annonc/mdu342. R17 3651 _____ Castellucci E, He T, Goldstein DY, Halmos B, Chuy J. DNA Polymerase e Deficiency Leading to an Ultramutator Phenotype: A Novel Clinically Relevant Entity. Oncologist. 2017;22(5):497-502. doi: 10.1634/theoncologist.2017-0034. Epub 2017 May 2. R17 3767 _____ Nebot Bral L, Brandao D, Verlingue L, Rouleau E, Caron O, Desprats E, et al. Hypermutated tumours in the era of immunotherapy: the paradigm of personalized medicine. Eur J Cancer. 2017;84:290-303. doi: 10.1016/j.ejca.2017.07.026. Epub 2017 Aug 29. R17 3823 _____ Luksza M, Riaz N, Makarov V, Balachandran VP, Hellmann MD, Selavyov A, et al. A neoantigen fitness model predicts tumour response to checkpoint blockade immunotherapy. Nature. 2017 Nov 8. doi:10.1038/nature24473. [Epub ahead of print]
Rationale for change	To remove references no longer used in the CSP.

Number of global amendment	6
Date of CTP revision	08 March 2021
EudraCT number	2017-005043-33
BI Trial number	1381.1
BI Investigational Product	BI 754091
Title of protocol	An open-label, Phase I trial to determine the maximum-tolerated dose and investigate safety, pharmacokinetics, and efficacy of BI 754091 in patients with advanced solid tumours.
To be implemented only after approval of the IRB / IEC / Competent Authorities	
To be implemented immediately in order to eliminate hazard – IRB / IEC / Competent Authority to be notified of change with request for approval	
Can be implemented without IRB / IEC / Competent Authority approval as changes involve logistical or administrative aspects only	
Additions to the text are bolded and deletions from the text are crossed off . Please note that formatting changes and minor changes to punctuation or spelling that do not affect meaning are not noted in this summary.	
Section to be changed	Title page

Proprietary confidential information © 2023 Boehringer Ingelheim International GmbH or one or more of its affiliated companies

Description of change	BI Investigational Product name Ezabenlimab added
Rationale for change	An official name, ezabenlimab , has been assigned to BI 754091 during the time after the last CTP version update.
Section to be changed	Title page
Description of change	BI Trial Clinical [REDACTED] name changed to [REDACTED]
Rationale for change	Change in TCM responsibility.
Section to be changed	Synopsis (Endpoints for the Phase Ia Dose Escalation, Safety Criteria); Sections: 4.1.5 Definition of dose-limiting toxicity, 5.1.1 Primary endpoints, 5.3 Assessment of Safety, 5.3.6.6 Severity of adverse events,
Description of change	CTCAE Version 4.03 added along with Version 5.
Rationale for change	Patients entered before amendment 4 used V4.03 and patients entered afterwards used V5.0.
Section to be changed	Synopsis (Endpoints for the Phase Ia Dose Escalation: Secondary, Endpoints for the Phase Ia Dose Expansion: Primary); 5.1.1 Primary endpoints; 5.1.2.1 Secondary endpoints of the Phase Ia (dose escalation) portion of the trial; 5.1.3. Further endpoints.
Description of change	Definition of Response (Objective Response) has been corrected to Confirmed Response (Confirmed Objective response) throughout the CTP.
Rationale for change	Clarification of the endpoint definition.
Section to be changed	Synopsis (Endpoints for the Phase Ia Dose Expansion: Secondary); 5.1.2.1 Secondary endpoints of the Phase Ia (dose escalation) portion of the trial.
Description of change	The following definitions for the safety endpoints were added: -Percentage of subjects with AEs -Percentage of subject with SAEs -Percentage of subjects with clinical relevant abnormalities in vital signs, laboratory evaluations or ECG parameters (note that clinically relevant abnormalities are those which have to be reported by the investigator as AEs).
Rationale for change	To clarify the precise definition of the safety endpoints.
Section to be changed	Section 3.3.4.2 Discontinuation of the trial by the sponsor.
Description of change	The following paragraph was added: “In case the trial is ended by the sponsor, the available clinical trial data will be analysed and reported approximately one year after the last patient has been enrolled. Patients who are still being treated with BI 754091 when the primary report of the trial is being prepared, will be kept on treatment in this trial and finalize the clinical observation period. Data of those patients will then be reported in a revised report and it will be noted in the primary report that such a revised report will be written.”

Rationale for change	Clarification of the data handling rules after trial discontinuation by the sponsor.
Section to be changed	Flow Chart 2 and Footnote "r"; Section 5.5.2.1 Biomarker assessments in blood samples; Table 10.4.2.1 and foot note 1.
Description of change	Footnote "r" was added: Only patients completed the activity up to until the cut of date for the primary report. All remaining patients will undergo EOT and 30 days visits safety procedures only. The following test was added: Only patients completed this activity up to until the cut of date for the primary report.
Rationale for change	After the trial discontinuation by the sponsor, PK/PD and biomarker sampling will not be collected for patients continuing in the study after the cut-off date for primary report DBL. These additional data are not anticipated to provide significant benefit to the patients or the sponsor.
Section to be changed	
Description of change	
Rationale for change	
Section to be changed	
Description of change	
Rationale for change	
Section to be changed	Section 5.4.1 Assessment of pharmacokinetics; Section 7.3.5 Pharmacokinetic and pharmacodynamic analyses
Description of change	Descriptions of the following BI internal SOPs deleted:

Proprietary confidential information © 2023 Boehringer Ingelheim International GmbH or one or more of its affiliated companies

	(001 MCS 36 472 RD 01 [2.0] and Venn Life Sciences SOP 'SOP 1.PKA.03 Non-compartmental PK/PD Analysis'). (001 MCS 36 472 RD 01 [actual version] and Venn Life Sciences SOP 'SOP 1.PKA.03 Non-compartmental PK/PD Analysis').
Rationale for change	During the trial conduct the SOPs were updated therefore the references listed in the CTP are not needed.
Section to be changed	Section 7.1.1 Statistical design – Phase 1a (dose escalation)
Description of change	The first cycle dose has been corrected in the paragraph below: “The objective of the Phase 1a portion of the trial is to determine the MTD and the RP2D. first cycle at dose d, d* = 800 3200 mg ”
Rationale for change	Mistake in writing has been corrected.

Number of global amendment	8
Date of CTP revision	07 March 2023
EudraCT number	2017-005043-33
BI Trial number	1381.1
BI Investigational Product	BI 754091
Title of protocol	An open-label, Phase I trial to determine the maximum-tolerated dose and investigate safety, pharmacokinetics, and efficacy of BI 754091 in patients with advanced solid tumours.
To be implemented only after approval of the IRB / IEC / Competent Authorities	
To be implemented immediately in order to eliminate hazard – IRB / IEC / Competent Authority to be notified of change with request for approval	
Can be implemented without IRB / IEC / Competent Authority approval as changes involve logistical or administrative aspects only	

Proprietary confidential information © 2023 Boehringer Ingelheim International GmbH or one or more of its affiliated companies

Additions to the text are bolded and deletions from the text are crossed off. Please note that formatting changes and minor changes to punctuation or spelling that do not affect meaning are not noted in this summary.
		
Section to be changed		Synopsis – Duration of treatment; Flow chart 1 and 2, foot note 1.
Description of change		
From: BI 754091 will be given on Day 1 of 21-day cycles for up to 1 year, or until progressive disease (PD) or unacceptable toxicity in the absence of other withdrawal criteria. If the patient is benefiting clinically at 1 year, he/she may continue after a case by case review with the sponsor.
 
To: BI 754091 will be given on Day 1 of 21-day cycles for up to 1 year, or until progressive disease (PD) or unacceptable toxicity in the absence of other withdrawal criteria. If the patient is benefiting clinically at 1 year, he/she may continue after a case by case review with the sponsor, but no longer than 31 August 2023.

Rationale for change		Treatment duration limitation added due to BI 754091 monotherapy program discontinuation.
Section to be changed		Section 3.1 Overall trial design and plan
Description of change		
Last sentence modified as follows: In addition, patients without PD may stay on trial after 1 year on a case-by-case basis after discussion with the Medical Monitor and the sponsor, but no longer than 31 August 2023. After this date treatment with the ezabenlimab will no longer be available.

Rationale for change		Treatment duration limitation added due to BI 754091 monotherapy program discontinuation.
Section to be changed		Section 3.3.4.2 Discontinuation of the trial by the sponsor
Description of change		
Addition: 5. Termination of the development program by the sponsor.

## **2 LIST OF ABBREVIATIONS**

See Medicine Glossary:

<http://glossary>

Term	Definition / description
ADA	Anti-Drug Antibody
AE	Adverse Event
AESI	Adverse Event of Special Interest
ALT	Alanine aminotransferase
ANCOVA	Analysis of Covariance
AST	Aspartate aminotransferase
ATC	Anatomical Therapeutic Chemical
AUC	Area Under the Curve
CI	Confidence Interval
CR	Complete Response
CT	Comcomitant Therapy
CTCAE	Common Terminology Criteria for Adverse Events
CTP	Clinical Trial Protocol
CTR	Clinical Trial Report
DCR	Disease Control Rate
DLT	Dose Limiting Toxicity
DoR	Duration of Response
ECG	Electrocardiogram
ECOG	Eastern Cooperative Oncology Group
eCRF	Electronic Case Report Form
EOT	End of Treatment
ICH	International Conference on Harmonisation
iCPD	Immune Confirmed Progressive Disease
iCR	Immune Complete Response
iORR	Immune Objective Response Rate
iPFS	Immune Progression-Free Survival
iPR	Immune Partial Response
iRECIST	Immune Response Evaluation Criteria in Solid Tumours

Term	Definition / description
iSD	Immune Stable Disease
iUPD	Immune Unconfirmed Progressive Disease
LLT	Lowest Level Term
Max	Maximum
MedDRA	Medical Dictionary for Regulatory Activities
Min	Minimum
MTD	Maximum Tolerated Dose
NE	Not Evaluable
OR	Objective Response
ORR	Objective Response Rate
OS	Overall Survival
PBMC	Peripheral Blood Mononuclear Cell
P25	25 th percentile
P75	75 th percentile
PD	Progressive Disease
PD	Protocol Deviation
PDc	Pharmacodynamics
PFS	Progression-Free Survival
PK	Pharmacokinetics
PKS	Pharmacokinetics Analysis Set
PR	Partial Response
PT	Preferred Term
Q1	Lower quartile
Q3	Upper quartile
P10	10th percentile
P90	90th percentile
RECIST	Response Evaluation Criteria in Solid Tumours
REP	Residual Effect Period
RO	Receptor Occupancy
RP2D	Recommended Phase 2 Dose
RPM	Report Planning Meeting
SAE	Serious Adverse Event

Term	Definition / description
SD	Stable Disease
StD	Standard Deviation
SOC	System Organ Class
TNBC	Triple Negative Breast Cancer
TS	Treated Set
TSAP	Trial Statistical Analysis Plan
WHO DD	World Health Organization Drug Dictionary

### **3. INTRODUCTION**

As per ICH E9, the purpose of this document is to provide a more technical and detailed elaboration of the principal features of the analysis described in the protocol, and to include detailed procedures for executing the statistical analysis of the primary and secondary variables and other data.

This Trial Statsitical Analysis Plan (TSAP) assumes familiarity with the Clinical Trial Protocol (CTP), including Protocol Amendments. In particular, the TSAP is based on the planned analysis specification as written in CTP Section 7 “Statistical Methods and Determination of Sample Size”. Therefore, TSAP readers may consult the CTP for more background information on the study, e.g., on study objectives, study design and population, treatments, definition of measurements and variables, planning of sample size, randomization.

SAS® Version 9.3 or a newer version and Phoenix TM WinNonlin ® version 6.2.1 will be used for PK analyses. SAS® Version 9.4 or a newer version will be used for all other analyses.

#### **4. CHANGES IN THE PLANNED ANALYSIS OF THE STUDY**

The CTP defines the primary endpoint in Phase Ia as number of patients experiencing DLTs graded according to Common Terminology Criteria for Adverse Events (CTCAE) Version 4.03 / 5.0 observed in the first cycle (3 weeks) in order to meet the objective of assessment of the maximum tolerated dose (MTD) of BI 754091. All patients in Phase Ia were assessed by CTCAE Version 4.03 and therefore CTCAE Version 5.0 is not applicable for the primary endpoint in Phase Ia.

## **5. ENDPOINTS(S)**

### **5.1 PRIMARY ENDPOINT(S)**

The primary objective of this study is to determine the safety and tolerability of BI 754091 as reflected by the primary endpoint MTD.

The primary endpoint of the Phase Ia dose-escalation portion of the trial is:

- Number of patients experiencing Dose Limiting Toxicities (DLTs) graded according to CTCAE Version 4.03, observed in the first cycle (3 weeks) in order to meet the objective of assessment of the MTD of BI 754091.

The number of patients with DLTs during the MTD evaluation period will be used to determine the MTD. The MTD is defined as the highest dose with less than 25% risk of the true DLT rate being above 33% during MTD evaluation period. For definition of DLTs, see CTP Section 4.1.5. The MTD evaluation period is defined as the first three weeks after a first administration of trial medication to BI 754091.

Patients who were replaced during the MTD evaluation period will not be considered for MTD determination. Those patients that have completed the MTD evaluation period without having been replaced will be referred to as patients evaluable for MTD determination (MTD set).

In addition, the primary endpoints of the Phase Ib dose-expansion portion of the trial are:

- Number of patients with DLTs observed during the entire treatment period, from the first infusion of study treatment to the date of last study treatment administration plus 30 days. See treatment period definition in [Table 6:1:1](#).
- Confirmed objective Response (OR), defined as the best overall response of confirmed complete response (CR) or partial response (PR) according to RECIST v1.1 assessed by the Investigator, where the best overall response is the best time point response recorded from the first administration of BI 754091 until the earliest of disease progression according to RECIST v1.1, death or last evaluable tumor assessment before start of subsequent anti-cancer therapy, loss to follow- up or withdrawal of consent.

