3. DESCRIPTION OF DESIGN AND TRIAL POPULATION

3.1 OVERALL TRIAL DESIGN AND PLAN

This is a Phase I, open-label, multi-centre trial of BI 754091 administered as a single agent. The trial design allows an escalation of dose with intensive safety monitoring to ensure the safety of the patients.

It is planned that approximately 15 patients with advanced solid malignancies will be enrolled in the Phase Ia portion of the trial, which will include dose-escalation of BI 754091 administered as monotherapy. The total number of patients will depend on the number of dose escalations necessary. Dose escalation will be guided by a BLRM with overdose control (EWOC). The BLRM estimates the MTD by updating estimates of the probability of observing a DLT in the MTD evaluation period (first 3 weeks) for each dose level in the trial as patient information becomes available. At no time in the trial, will it be permitted to escalate to a dose which does not fulfil the EWOC principle (refer to Section 7).

Successive cohorts of patients will receive doses of BI 754091 until the MTD is reached. A cohort size of 3 patients will be treated at each dose level. Additional patients (up to 6 more) could be added to some previously evaluated cohorts to expand the safety and PK evaluation. After all patients in a cohort have either experienced a DLT or have been observed for at least the MTD evaluation period (first 3 weeks) without experiencing a DLT, the Bayesian model will be updated with the newly accumulated data. The overdose risk will then be calculated for each dose, and escalation will be permitted to all doses which fulfil the EWOC criterion. Hypothetical data scenarios (see example in Section 10.5.1) will be calculated with potential cohort sizes and presented at the meetings with the Safety Review Committee (SRC, see Section 3.1.2). Based on the model and on additional information (PK, pharmacodynamics [PDc], patient profiles), the members of the SRC will reach a joint recommendation on the next dose level to be investigated and the size for the next dose-escalation cohort. However, the final decision on the next dose level and cohort size will be made mutually between the BI Clinical Program Leader and the SRC.

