4.1.7 Definition of evaluable patient

For decisions on dose escalation, an evaluable patient is defined as a patient who has received BI 754091 and either:

- has completed the minimum safety evaluation requirements during the first cycle (first 3 weeks)

OR

- has experienced a DLT during the first cycle (first 3 weeks).

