5. VARIABLES AND THEIR ASSESSMENT

5.1 TRIAL ENDPOINTS

5.1.1 Primary endpoints

The primary endpoint of the Phase Ia dose-escalation portion of the trial is:

- Number of patients experiencing DLTs graded according to CTCAE Version 4.03 / 5.0 observed in the first cycle (3 weeks) in order to meet the objective of assessment of the MTD of BI 754091.

The MTD is defined as the highest dose with less than 25% risk of the true DLT rate being above 33%. For definition of DLTs, refer to Section 4.1.5.

A BLRM employing the EWOC principle will be used during the escalation phase for selection of doses to investigate and for estimation of the MTD. Cohorts of patients will receive escalating doses of BI 754091 until the MTD is reached. Each cohort will consist of newly enrolled patients. Estimation of the MTD during the escalation phase of the trial will be based upon the estimation of the probability of a DLT in Cycle 1 in the set of evaluable patients for MTD. The corresponding methodology is described in Section 7 and Appendix 10.5. The MTD estimate established during the dose escalation phase will be re-investigated after the expansion phase by re-running the BLRM including all data from escalation and expansion phase, in particular also considering the DLT information from all treatment cycles.

The primary endpoints of the Phase Ib dose-expansion portion of the trial are:

- Number of patients with DLTs observed during the entire treatment period.
- Confirmed Objective Response (OR), defined as the best overall response of confirmed complete response (CR) or partial response (PR) according to RECIST v1.1 as assessed by the Investigator

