7.3 PLANNED ANALYSES

For the determination of the MTD, only MTD-evaluable patients will be considered. For other analysis of efficacy and safety endpoints, all patients in the treated set (i.e., patients treated with at least one dose of trial medication) will be included in the analysis. Any other analysis sets will be defined in the Trial Statistical Analysis Plan (TSAP).

No per protocol set will be used in the analysis. However, important protocol violations will be summarised with details specified in the TSAP.

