7.3.1 Primary endpoint analyses

In order to identify the MTD of the trial, the number of patients with DLTs at each dose level during the Phase Ia MTD evaluation period (first three weeks) must be presented. Patients who discontinue during the first treatment course for reasons other than a DLT will be excluded from the determination of the MTD.

In addition, the number of patients with DLTs that occurred during the entire treatment period, including Phase Ia and Phase Ib, will be summarised at each dose level. The BLRM will be rerun to re-evaluate the MTD and RP2D together with all relevant data collected during Phase Ib.

For the primary efficacy endpoint of Phase Ib, objective response rate (ORR) will be summarised and presented with 95% two-sided confidence intervals using the Clopper-Pearson method.

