#### **MTD set:**

This patient set includes all patients enrolled in a Ia dose finding cohort of the trial who were not replaced within the MTD evaluation period

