## **7.4 PRIMARY ENDPOINT(S)**

### **7.4.1 Primary analysis of the primary endpoint(s)**

In order to identify the MTD and the recommended dose for the Phase Ib dose expansion phase, the number of patients with DLTs at each dose level during the Phase Ia MTD evaluation period (first three weeks) must be presented. Patients who discontinue during the first treatment course for reasons other than a DLT will be excluded from the determination of the MTD.

The analysis of the MTD is based on a BLRM guided by the escalation with overdose control principle. The MTD is defined as the highest dose for a given schedule that is expected to cause less than 25% risk of the true DLT rate being above or equal to 33% during the MTD evaluation period. Estimation of the MTD during the dose escalation phase of the study will be based upon the estimation of the posterior probability of the incidence of DLT in toxicity categories during the MTD evaluation period for all evaluable patients. The model to be used is specified in CTP Section 7.

Tables and bar charts displaying the posterior probabilities of the true DLT rates being in either the underdosing interval, the targeted toxicity interval or the over toxicity interval will be produced.

For Phase Ib dose expansion, OR according to RECIST v1.1 will be analysed in terms of

objective response rate (ORR), defined as the proportion of patients with best overall response of CR or PR. ORR according to RECIST v1.1 will be summarised descriptively with 95% exact Clopper-Pearson confidence intervals (CIs).

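### The SAP gives two different definitions of the MTD set, neither matching protocol 4.1.7; read literally, SAP 5.1 drops a patient whose Cycle 1 DLT ends in death or leaving the trial before week 3

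*SAP*

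**What the plan says.** **Protocol.** Section 7.3 states: "For the determination of the MTD, only MTD-evaluable patients will be considered". Section 5.1.1 likewise estimates the MTD "in the set of evaluable patients for MTD". The definition of an evaluable patient is in section 4.1.7: BI 754091 received, and either the minimum Cycle 1 safety evaluation completed or the patient "has experienced a DLT during the first cycle (first 3 weeks"). Section 3.1 uses similar logic for the model update, which requires everyone at that dose level to "have either experienced a DLT or have been observed for at least the MTD evaluation period (first 3 weeks) without experiencing a DLT". Section 7.3.1 adds an exclusion: "Patients who discontinue during the first treatment course for reasons other than a DLT will be excluded from the determination of the MTD". Section 3.3.4.1 says that patients who leave because of a DLT are not replaced. It allows replacement, after discussion, of patients who withdraw for another reason or miss more than one Cycle 1 visit, if this makes them non-evaluable for PK or for safety.

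**SAP.** Section 5.1: "Those patients that have completed the MTD evaluation period without having been replaced will be referred to as patients evaluable for MTD determination", and it labels this group the MTD set. Section 6.3 says that the MTD set "includes all patients enrolled in a Ia dose finding cohort of the trial who were not replaced within the MTD evaluation period". Section 7.4.1 repeats the protocol 7.3.1 exclusion and bases the MTD on "estimation of the posterior probability of the incidence of DLT in toxicity categories during the MTD evaluation period for all evaluable patients", without defining evaluable. Section 7.8 removes replaced patients from the MTD determination. Section 4 declares one change from the protocol, the CTCAE version.

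**The concern.** Two SAP sections give a programmer different membership rules for one named set, and neither is the protocol's rule. There are three separate departures:

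1. SAP 5.1 requires completion of the three weeks and has no DLT alternative. An early-exit DLT patient, the most informative kind of patient for an MTD, falls out on a literal reading.
2. SAP 6.3 requires only enrolment and non-replacement. A patient who fails protocol 4.1.7 but was not replaced stays in and counts as DLT-free.
3. SAP 5.1, 6.3 and 7.8 all use replacement as the criterion. A patient replaced only because PK was not evaluable is removed even though protocol 4.1.7 is met.

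The protocol also leaves one case open. A patient who met the minimum safety evaluation and then discontinued in Cycle 1 for a non-DLT reason is evaluable under 4.1.7 but excluded by 7.3.1.

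At stake are the Phase Ia primary endpoint and the reported posterior toxicity probabilities. These rest on about 15 patients, so one patient can matter.

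**Working it through.** **Step 1: membership by patient type.** Each definition is applied as written, before the separate SAP 7.4.1 exclusion.

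| Phase Ia patient | SAP 5.1 | SAP 6.3 | Protocol 4.1.7 |
|---|---|---|---|
| Completes three weeks, no DLT, not replaced | in | in | in |
| Cycle 1 DLT, still observed at week 3 | in | in | in |
| Cycle 1 DLT, dies or leaves before week 3 | **out** | in | in |
| Dosed, no DLT, leaves before minimum evaluation, not replaced | out | **in** | out |
| Enrolled, never dosed, not replaced | out | **in** | out |
| Completes minimum evaluation and three weeks, no DLT, replaced for PK only | **out** | **out** | in |
| Leaves before minimum evaluation, no DLT, replaced | out | out | out |

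The two SAP definitions disagree on three rows (3, 4 and 5). SAP 5.1 departs from protocol 4.1.7 on two (3 and 6), and SAP 6.3 on three (4, 5 and 6).

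**Step 2: model inputs.** From protocol 7.1.1 and Table 7.1.1.1: 1:

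- Model: logit p(d) = log α + β·log(d/800).
- Prior on (log α, log β): weight 0.9 on a normal with mean (−4.855, 1.062), and weight 0.1 on a normal with mean (−0.578, 0.028). Both have SDs (2, 1) and correlation 0.
- Overdose: p(d) ≥ 0.33. EWOC: posterior P(overdose) < 0.25.
- Doses examined: 80, 160, 240, 320, 400, 480, 560, 640 and 800 mg.
- Posterior ∝ prior × ∏ p(d)^r (1−p(d))^(n−r), integrated on a 2401 × 2401 grid.

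**Step 3: reproduce the protocol's figures (Table 10.5.1: 1).**

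| Scenario | Quantity | Protocol | Recomputed |
|---|---|---|---|
| 6 | under/target/over at 400 mg | 0.406/0.399/0.195 | 0.416/0.389/0.195 |
| 5 | P(overdose) at 800 mg | 0.170 | 0.171 |
| 5 | P(overdose) at 400 mg | 0.033 | 0.031 |
| 4 | P(overdose) at 560 mg | 0.212 | 0.206 |

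Scenario 3 does not reproduce (0.121 against 0.186 at 240 mg) and is not used.

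**Step 4: change one patient in Scenario 6.** The data are 0/3 at 80 mg and 1/6 at 240 mg, plus the count shown at 400 mg. Entries are P(overdose).

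| Count at 400 mg | 320 | 400 | 480 | 560 | 800 | Highest dose meeting EWOC |
|---|---|---|---|---|---|---|
| 1/3 | 0.108 | 0.195 | 0.282 | 0.356 | 0.508 | 400 |
| 0/2 | 0.024 | 0.048 | 0.079 | 0.112 | 0.206 | 800 |
| 1/2 | 0.164 | 0.269 | 0.362 | 0.436 | 0.579 | 320 |
| 1/4 | 0.072 | 0.141 | 0.219 | 0.290 | 0.446 | 480 |

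- *Departure 1.* The early-exit DLT patient is counted under 4.1.7 (1/3) and dropped under SAP 5.1 (0/2). P(overdose) at 400 mg falls from 0.195 to 0.048, so toxicity is understated.
- *Departure 2.* A non-evaluable DLT-free patient is left out under 4.1.7 (1/2) and kept under SAP 6.3 (1/3). The value at 400 mg goes from 0.269 to 0.195, crossing the 0.25 limit, so toxicity is again understated.
- *Departure 3.* A DLT-free patient is replaced for PK only, and the new patient is also DLT-free. Both count under 4.1.7 (1/4), only one under the SAP (1/3). The value goes from 0.141 to 0.195, so toxicity is overstated.

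**Step 5: a single-DLT dataset.** Scenario 4 has one DLT, at 240 mg. If that patient is dropped (0/5 there), P(overdose) at 240 mg falls from 0.033 to 0.000. The protocol's requirement of at least one DLT for an MTD is then no longer met.

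**The case against.** The strongest reply is that nobody intended to drop a DLT patient. SAP 5.1 itself says that the number of patients with DLTs in the evaluation period determines the MTD, and the exclusion it states is for replaced patients, which DLT leavers never are. SAP 6.3 keeps them, and SAP 7.4.1 excludes only non-DLT discontinuations. This stands as evidence of intent. It also shows that the defining sentence in SAP 5.1 conflicts with the rest of the SAP.

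Second, protocol 4.1.7 is framed for escalation decisions, and protocol 7.3 does not cite it. That is so, but it is the protocol's only definition of an evaluable patient, and 5.1.1 and 7.3 both rely on that concept.

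Third, SAP 7.4.1 already removes many patients in departures 2 and 3, namely those who discontinued for a non-DLT reason. That is right. What remains is mainly patients who stayed on trial but missed visits, and the replacement decision must then diverge from 4.1.7.

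Fourth, no MTD is declarable in any of the illustrations. They have 11 to 13 patients and at most 4 at 400 mg, and the largest target-interval probability in any of them is 0.389, against the required 0.50. This also stands. The figures show a shift in the highest dose meeting EWOC, not a changed MTD.

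**Conclusion.** The concern holds. SAP 5.1 and 6.3 define one set in two ways, and neither is protocol 4.1.7. On a literal reading, SAP 5.1 removes an early-exit DLT patient from the primary-endpoint population. In the Scenario 6 illustration, that one patient moves P(overdose) at 400 mg from 0.195 to 0.048 and the highest tabulated dose meeting EWOC from 400 to 800 mg. The other two departures move the same probability by about 0.05 to 0.07, in opposite directions. These are sensitivity figures on hypothetical counts and say nothing about which dose is right.

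The exposure is limited. Departure 1 needs death or leaving the trial within 21 days, because a patient who only stops drug still has a follow-up visit 30 days after the last dose. Live escalation is governed by protocol 4.1.7, and DLT tables on the treated set are unaffected. The documents do not show that any patient falls in the disputed categories. The point should be corrected because a stated rule for the primary-endpoint population is wrong as written, not because a reported result is known to be wrong.

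**What to change.** - In SAP 6.3, define the MTD set once: treated Phase Ia patients who meet protocol 4.1.7, including every patient with a Cycle 1 DLT whether or not the three weeks were completed.
- In SAP 5.1, SAP 7.4.1 and the MTD clause of SAP 7.8, replace the local wording with a reference to that set. Keep replaced patients in all other safety evaluations.
- Reconcile the set with the exclusion shared by protocol 7.3.1 and SAP 7.4.1. State whether a patient who met the minimum safety evaluation and then discontinued in Cycle 1 for a non-DLT reason is in or out.
- Record any resulting departure from protocol 4.1.7 or 7.3.1 in SAP section 4.

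The cost is wording in four SAP sections, one decision, and possibly one entry in section 4. No new data are needed.
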